## Purpose of the Study

The purpose of this study is to develop a multiplexed low coherence interferometry (mLCI) endoscopic probe for mapping the epithelial types of the cervix. This vaginal mLCI probe will obtain optical measurements from the cervix. These measurements can be used to create a map of the surface cells that distinguishes ectocervical epithelia, endocervical epithelia, and the squamocolumnar junction (t-zone) between them, which is the region where cervical dysplasia is most likely to occur.

The research study described here will be a preliminary study to evaluate the performance of the mLCI device for detection of cervical dysplasia. The results from a small study at Duke will help to optimize the function of the mLCI instrument before completing a larger study with collaborators at Jacobi Medical Center (see *Background & Significance* below). The device will be studied in a larger subject population at Jacobi to determine how effectively it can distinguish the types of cervical epithelia.

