### **Study Procedures for subjects at Jacobi**

Subjects will be informed of the study when they present to the clinic for a regular clinical care visit. If interested in participating, subjects will complete the following study-related procedures in addition to the standard of care visit procedures.

- Read consent form
- Ask / answer questions
- Sign consent form
- Urine pregnancy test – must be negative before imaging can occur
- Colpophotography of cervix to compare with mLCI data
- mLCI examination of the cervix (with speculum)

We will obtain written informed consent and confirm eligibility criteria. Data collection will include a brief medical history and pregnancy testing.

The doctor will then insert a speculum in order to directly visualize the cervix. Colpophotographs will be taken to compare to mLCI data during data analysis. The doctor will then gently place the mLCI probe against the cervix. White light camera visualization, incorporated into the mLCI probe, will guide the probe positioning by the clinician to confirm contact with the cervical epithelium. The probe will then be held in place for mLCI data acquisition for up to 1 minute. When data collection is completed, the mLCI probe will be removed and placed on a custom holder that prevents the contact portions of the probe from coming into contact with contaminating surfaces.

The doctor will then continue with the rest of the patient's standard of care visit procedures.

At some visits, the physician may choose to make an additional measurement with the mLCI device, by inserting it without a speculum and using the white light camera (incorporated into the mLCI probe) for visual guidance to position the probe. Comparing measurements made by inserting the mLCI device with and without a speculum will allow us to determine if the white light visualization by the camera is sufficient to correctly place the probe over the cervix without having to use a speculum in future studies.

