### **Selection of Subjects at Duke**

This project will recruit healthy women who:

- are able to provide informed consent
- are at least 21 years old
- are willing to abstain from sexual intercourse for at least 24 hours before the study visit

Participants meeting any of the following exclusion criteria will be excluded from taking part in this study. Women must not:

- be pregnant
- have given birth to a baby
- have a current gynecologic infection or discharge
- be using an IUD
- have had any cervical surgery
- have had medical or cosmetic surgery involving the reproductive organs or genitals within the past 6 months
- be currently enrolled in any research studies involving the application of vaginal formulations
- be employed or supervised by the study investigators
- have any other condition that, in the opinion of the study clinician, would contraindicate participation in the study

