## **Data Analysis & Statistical Considerations**

### ***Data analysis for Duke site***

The proposed study is designed as a pilot study, intended to provide feasibility and usability data to inform future studies on a larger scale. The planned pilot study will include 10 subjects, which will yield success/failure metrics of the probe design with 10% precision. Elements of the probe performance that will be evaluated include ease of use by the medical practitioner, patient comfort, ability to access the relevant anatomy, and quality of mLCI imaging data. Because the goal of the pilot study is the evaluation of general feasibility, no subject data will be excluded if no predetermined exclusion criteria are met.

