### ***Data analysis for Jacobi site***

Construction of epithelium maps by mLCI: Maps of the cervix delineating the T-zone will be created from each subject's mLCI data. The extent of columnar and squamous epithelia will be reported as a percentage of the image of the epithelium. Each scan in the 36 point field will initially be reviewed manually to determine the epithelium type based on the depth-resolved reflection profile for that point. The presence of clear histological layers is indicative of squamous epithelium while a thinner layer with less structure indicates columnar epithelium [22]. As we compile a database of mLCI maps of the cervix, we will develop automated algorithms for assessing epithelial types and transitions by using cluster analysis to discriminate scans. The mLCI maps will be compared to digital colposcopy analysis to assess accuracy.

Measurement of epithelial areas by colposcopy: Digital colposcopic images will be viewed in Adobe Photoshop for quantitative computerized planimetry as previously published [23, 24]. We will manually outline all areas of columnar, metaplastic and squamous epithelia and the total visible cervical face. Total pixel counts of the various epithelial types will be calculated and ectopy expressed as percentage of the total cervix.

Correlation of mLCI images to colposcopy and detailed written maps: The mLCI epithelial maps will be visually compared to colposcopic images to achieve co-registration. This is feasible based on the relatively modest number of patients in the study. The written map and white light imaging via the probe will aid in coregistration. We will correlate mLCI readings with calculated areas of epithelial types (pixel counts and percentage). Biostatistical analyses will address covariates including age, infections, cytology, menstrual cycle, and sexual behaviors.

Potential problems, alternative strategies, and benchmarks for success: The mLCI approach will be viewed as successful if there is less than average absolute difference of 10% in the area estimate compared with manual analysis.

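### Does the Purpose section's mention of detecting cervical dysplasia commit the study to a diagnostic result that it does not plan to produce?

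*Combined protocol and SAP*

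**What the plan says.** The second paragraph of the Purpose of the Study section describes the research as "a preliminary study to evaluate the performance of the mLCI device for detection of cervical dysplasia". The section's first sentence gives the purpose as building a probe that maps epithelial types, and its last gives the aim of the larger Jacobi part as "to determine how effectively it can distinguish the types of cervical epithelia".

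The later sections describe the following work.

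- **Duke.** The eligibility list begins "This project will recruit healthy women who". The analysis is a pilot, "intended to provide feasibility and usability data to inform future studies on a larger scale". It looks at ease of use, comfort, access to the anatomy and quality of the imaging data.
- **Jacobi.** Under the study procedures, "Colpophotographs will be taken to compare to mLCI data during data analysis". Under the data analysis, "Maps of the cervix delineating the T-zone will be created" from each subject's scans, and "The mLCI maps will be compared to digital colposcopy analysis to assess accuracy". Success is an average absolute difference in area below 10% against manual analysis.
- **Cytology.** It enters the analysis once, in a list: "Biostatistical analyses will address covariates including age, infections, cytology, menstrual cycle, and sexual behaviors".

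**The concern.** The sentence is about this study, not the wider research programme, and the word preliminary limits its scale rather than what is being evaluated. Read literally, it announces an estimate of diagnostic performance for dysplasia. Such an estimate needs three things: a dysplasia call from the device, a reference standard for dysplasia, and an analysis such as sensitivity and specificity. The document describes none of them.

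The stake is interpretation. Two IRBs oversee the study, and readers look to the Purpose section to learn what a study will show. Good agreement on epithelial area could later be presented as evidence that mLCI detects dysplasia, which the planned analysis would not support.

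**Working it through.** No arithmetic applies, and the plan states no figure for dysplasia detection that could be reproduced. The check has two parts: set the sentence beside the rest of the document, then ask what would differ if it were reworded.

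**1. Where dysplasia appears.** From the mLCI instrument section to the end of the main text, dysplasia is named in two places. One is the instrument description, which explains why the squamocolumnar junction matters. The other is Potential Benefits, which describes a possible future use. It is not named in the study procedures at either site, in Duke eligibility or in either data analysis section. Biopsy, sensitivity and specificity do not occur anywhere in that stretch.

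**2. What each planned comparison measures.**

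- Duke probe performance: four elements of usability and data quality.
- Placement with and without a speculum (all Duke subjects, some Jacobi visits): whether the white-light camera alone can guide the probe.
- Jacobi point readings: each point of the 36-point field is classed as squamous or columnar from its depth profile, with automated clustering to follow.
- Jacobi reference: columnar, metaplastic and squamous areas outlined on colposcopic images. Dysplastic areas are not outlined.
- Jacobi correlation and benchmark: mLCI readings against those areas, with the 10% limit on the area difference.

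All of these concern feasibility, placement or epithelial type and area. They agree with one another, with the first and last sentences of the Purpose section, and with the purpose stated for the instrument. The phrase about dysplasia is the outlier.

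**3. What would change if the phrase named epithelial mapping instead.**

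- *Population:* unchanged. Duke would still enrol healthy women, and selection at Jacobi would still rest with that site.
- *Reference:* unchanged. It is colposcopic planimetry.
- *Sample size:* unchanged. The 10 Duke subjects are justified by precision on success or failure of the probe design. The target of 40 completers at Jacobi is not tied to a number of dysplasia cases.
- *Analyses and covariates:* unchanged.
- *Success rule:* unchanged. It is already restricted to area.

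The wording therefore has no effect on any result the study will report.

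**The case for a change.** The strongest argument for a change is that the correction costs one phrase and prevents a misreading. The Background assigns mLCI a role in flagging regions likely to harbour dysplasia, and that role is not tested here. A reader who combines that ambition with the disputed sentence could expect diagnostic evidence. Leaving an inaccurate purpose in place has no merit of its own.

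Part of this stands: the sentence is inexact, and the analysis sections do not rescue its literal meaning. Three things limit its force.

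- The misreading is corrected within the same section, which names epithelial mapping before and after the disputed sentence. Potential Benefits calls the work early feasibility, and the responsibilities section limits the protocol to the grant's first specific aim. In that setting the phrase reads more naturally as the device's intended use.
- It would go too far to say that the study cannot yield information on dysplasia. Subject selection at Jacobi is left to that site, its standard-of-care procedures are not itemised, and cytology is expected among the covariates. The document supports only the statement that no such analysis is planned.
- A longer replacement could bring mismatches of its own. Assigning feasibility to Duke alone would overlook speculum-free placement at Jacobi. Promising accuracy for the junction itself would name a quantity for which the analysis section gives no location metric.

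**Conclusion.** The inconsistency is genuine but clerical. One phrase in the Purpose section is broader than the planned work, while the rest of that section, the instrument description, the procedures and the analyses agree on feasibility and epithelial mapping. The effect on procedures, sample sizes, analyses and the 10% area benchmark is nil, so no change to the plan is called for.

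This rests on two assumptions: that the analysts follow the data analysis sections as written, and that reports state the conclusion in terms of epithelial type and area. If a report claimed performance in detecting dysplasia from the area comparison, the fault would lie with that claim; the planned analysis makes none.

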## Background & Significance

**Clinical problem:** Cervical cancer, caused by persistent human papillomavirus (HPV) infection, is the second most common female malignancy worldwide. An estimated 500,000 new cases are diagnosed annually, including 12,170 new cases in the U.S in 2012, which reflects an age-adjusted incidence of 8.1 per 100,000 women [1]. Given that cervical cancer typically develops over many years, the early detection of cervical dysplasia (pre-cancers) affords a critical opportunity for treatment and thus prevention of life threatening invasive cancer. In developed countries, the availability of cervical cytology (Papanicolaou smear) for routine screening and colposcopy-directed biopsy for diagnosis has led to decreases in incidence and mortality rates [2]. However, despite their important impact, cytology and colposcopy remain very limited in their sensitivity, specificity, and interobserver reproducibility [3, 4]. The accurate identification of dysplastic areas of the epithelium is challenging and hence clinical guidelines recommend frequent patient screening schedules [5, 6] that are particularly difficult to implement in developing countries. *The need for more effective evaluation tools persists.*

**Potential Solution:** We propose to address this need by creating an imaging platform that uses *coherence imaging* to evaluate cervical tissues at two length scales. At the millimeter (tissue) scale, a multiplexed LCI (**mLCI**) approach will use multiple imaging channels to efficiently map the cervical epithelium to identify histological structures and red-flag suspicious regions, likely to harbor dysplasia. We have shown that mLCI can survey large areas of tissues *in the female reproductive tract* to obtain diagnostic information on coating by drug delivery gels [7, 8]. Once mLCI identifies suspicious areas, angle-resolved LCI (**a/LCI**) will obtain high resolution, depth resolved nuclear morphology measurements on the micron (subcellular) scale [9, 10]. We have shown that a/LCI can detect dysplastic lesions *in vivo* in the esophagus [11] and *ex vivo* in other types of epithelia such as colon [12] and trachea [13]. The combination of these two optical technologies, mLCI and a/LCI, will provide a unique platform for comprehensive assessment of the cervix at both tissue and subcellular scales. The novel technology will impact clinical detection of cervical dysplasia as well as support clinical and translational research on the fundamental biology of the cervical epithelium.

**Rationale for collaborative project:** The Duke team has had significant success in developing endoscopic imaging modalities for detection of precancerous tissues. Ongoing collaboration between the group in Duke BME and the Department of Ob/Gyn at Duke University Medical Center (DUMC) has produced important studies of the pharmacology of anti-HIV microbicides delivered to the lower female reproductive tract [7, 8, 14-17]. Here we seek to forge a broader collaboration to bring together the established team at Duke with a leading group in clinical research at Jacobi Medical Center. Jacobi serves a predominately minority population, and due to the largely immigrant status of women over age 26, HPV vaccination rates are low. Therefore, it has a large population of women with HPV-associated cervical dysplasia and a significant number of women with cervical cancer.

This collaboration will create a powerful combination of technology development and translation at the leading edge of gynecological biomedicine. This project will develop and test new instruments for cervical imaging at Duke and field test these technologies in the large, diverse patient population available at Jacobi Medical Center. The anticipated outcome is the creation of a diagnostic imaging tool that can screen women for cervical precancers and cancers and/or triage precancerous lesions in women who have had a positive cytology test.

## **INNOVATION**

**Novel multimodal imaging platform that combines mLCI and a/LCI:** The mLCI technology is unique in its ability for depth resolved imaging of *wide areas* of tissues. While LCI can obtain high resolution tomographic images at micron scales, as is done in optical coherence tomography (OCT), that approach is limited by often cumbersome scanning mechanisms and the large volume of data generated. Instead, mLCI uses sparse sampling and multiple parallel channels to more efficiently scan wider tissue areas. We will exploit this ability to create a new modality for quickly mapping the cervical epithelium, analogous to the function of colposcopy, but with improved performance. This is a particular challenge due to the complex combination of cervical epithelial types that are often in transitional states (columnar to metaplastic to squamous). As a counterpart to the mLCI, the a/LCI modality will combine the depth resolution and penetration of OCT with the sensitivity to subcellular structure that is obtained via light scattering, providing a function analogous to biopsy. Our group has recently validated a/LCI as an *in vivo* method for identifying dysplastic esophageal tissues [11]. Although prior research has applied OCT and light scattering to cervical dysplasia [18, 19] these approaches have not been clinically feasible. The unique capabilities of a/LCI, which enable high accuracy in detecting dysplasia, offer a significant potential for clinical translation. By combining mLCI and a/LCI into a single integrated platform, we will capitalize on recent trends in multimodal imaging. As identified by clinicians and researchers in multiple fields [20, 21], optimal screening methods can be realized by using a wide area scan to survey for suspicious regions in tandem with a high resolution modality to further diagnose those regions. Thus, we will implement this paradigm and create a hybrid imaging modality that integrates tissue and cellular imaging data. The unique power of this multimodal LCI device will lie in its ability to accurately identify dysplastic and cancerous tissues against the background of the complex tissue types that comprise the cervical epithelium.

**Innovation in clinical care of cervical disease:** In the clinic, the clear advantage of the multimodal LCI platform will be its ability to support clinical decision-making without relying on gross clinical colposcopic impression, the traditional but somewhat subjective diagnostic method. Further, the potential to provide reliable “real-time” information to the clinician would allow immediate treatment of epithelial abnormalities. We expect this

device to be uniquely applicable to women of all ages in contrast to the recent implementation of screening biomarkers such as HPV DNA testing which are restricted to older women. Our field trials will access the diverse patient population found at Jacobi OB/GYN. This population represents the full spectrum of cervical health, including healthy young women and those with incident HPV infection, persistent HPV infection, benign cervical lesions, cervical precancers, and cancer. Our proposal to develop an accurate and efficient tool for cervical cancer screening will rely on its ability to detect disease in the setting of complex tissue compositions inherent to the cervix—the downfall of many prior optical technology attempts. Innovation is inherently risky; however our combined expertise in coherence imaging and the clinical study of the cervical epithelium will support the success of the proposal.

### **Multi-site Study: Responsibilities**

[name], the Duke PI of this study, is the primary awardee of the NIH grant supporting this work. [name] and his team have developed the mLCI research device and will conduct a small study at Duke (described below) to assess if any adjustments to the device are needed before it is sent to Jacobi Medical Center for the larger study. The study at Jacobi Medical Center will be funded as a subaward / consortium agreement of [name] NIH grant. The research proposed in this study protocol addresses Specific Aim 1 of the NIH grant.

Duke will recruit up to 15 women to enroll in this study, in order to achieve the target number of 10 subjects who complete the study at that site. Jacobi will enroll up to 100 women for this study, in order to achieve the target number of 40 women who complete the study at that site. Data from both sites will be analyzed at Duke. Data received from Jacobi will be de-identified before being sent to Duke. Study conduct at Duke will be under the oversight of the IRB of the Duke University Health System. Study conduct at Jacobi Medical Center will be under the oversight of the IRB of the Albert Einstein College of Medicine and Montefiore Medical Center.

### **Design & Procedures**

#### **mLCI instrument**

The purpose of this instrument is to obtain optical measurements from the cervix via a vaginal probe to create a map of the surface cells that distinguishes the ectocervical and endocervical epithelia. The boundary between the two cell types is known as the squamocolumnar junction, or “t-zone”, which is the transitional region at which cervical dysplasia is most likely to occur.

The instrument delivers infrared light to 36 locations on the cervix, and measures the depth-profile of back-scattered light from each location using low coherence interferometry (LCI). This technique is thus termed multiplexed LCI (mLCI). The LCI profile data is stored by a computer for subsequent analysis to identify cell type.

The components of the mLCI instrument are grouped in the following modules: 1) Optical probe, 2) mLCI interferometer, 3) white light imaging module, 4) computer, and 5) physical enclosure.

#### ***Optical Probe***

The optical probe is primarily cylindrical in form, with a diameter of approximately 25 mm and a rigid length of approximately 270 mm. The probe housing is fabricated by a 3D printing process known as fused deposition modeling (FDM). The material is MED-610 (Stratasys Inc., Eden Prairie, MN), a transparent polymer certified as biocompatible.

The adhesives used on the external seams of the probe are Silastic Medical Adhesive Type A (Dow Corning, Midland, MI), a soft silicone adhesive. A 36-channel single-mode fiber bundle is contained within the probe housing, as well as several glass optical elements for imaging. The rounded tip of the probe is intended to contact the cervical surface, and the focus of mLCI imaging is located on the plane of this tip.

The probe also contains fiber optics that deliver white LED illumination to the region of imaging and collects wide-field imaging information through a fiber bundle to provide real-time video endoscopic guidance for probe placement.

A flexible tether containing the 36-fiber bundle and white light optical fibers protrudes from the proximal end of the probe and is connected to the mLCI interferometer and white light imaging modules, respectively.

The full length of the probe is not intended for vaginal insertion. A demarcation line approximately 220 mm from the probe tip indicates the line beyond which the probe should not be inserted. High-level disinfection procedures as described in this document will be performed up to the line.

The probe contains no electrical components or wires.

